Unfortunately, despite a significant impulse in the medical community to move towards an "individualized medicine" approach to patient centered treatment, the current clinical treatment strategy is based on a set algorithm which does not take into account individual patient differences. Rather, physicians are guided to choose a drug (one out of many options) in a given class of drugs and use that specific drug as a "first line therapy" (typically initiating with the diuretic class) and titrate that specific drug of choice to therapeutic dosage regardless of efficacy². It is only after a prolonged course of treatment with that specific class of drug that clinical efficacy is determined (typically three months). At this stage, if clinical guideline goals for blood pressure have not been met, it is often recommended that the patient remain on the "first line therapy" whilst an additional drug from a different class of drugs (typically an Angiotensin converting enzyme inhibitor (ACE inhibitor) or Angiotensin II receptor blocker (ARB)) is added to the

PROTOCOL TITLE:**VERSION DATE:**

pharmacologic regimen. Again, this drug is titrated to recommended therapeutic dosage and another prolonged course of treatment is initiated before clinical efficacy is determined (an additional three months – six months since initiation of treatment). If at this point, clinical guideline goals for blood pressure have not been met, a third drug from a third class of drugs (typically a beta-blocker) is added and the process is repeated (another three months – nine months from initiation of treatment). Further, if clinical guideline goals have continued to be elusive, the diagnosis of refractory hypertension is added and the process is reinitiated with a different combination of drugs, different classes of drugs, different drug options within a given class of drugs, different dosages, or all of the above. Thus, from the time of initial diagnosis and the start of treatment to the point in which blood pressure is adequately controlled may take anywhere from three months to well over one year. This trial-and-error standard of care is clearly not optimal.

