3.0 Study Endpoints/Events/Outcomes

1. Primary Endpoint/Event/Outcome:

To assess the effectiveness of the use of a patient’s genes to predict which hypertension therapy is successful, as measured by:

1. Level of blood pressure control (<140/<90)
2. Change in blood pressure from baseline to control

2. Secondary Endpoint(s)/Event(s)/Outcome(s):

Blood Pressure control with respect to:

1. Number of medications needed to obtain control
2. Time to control
3. Number of office visits to control
4. Side effects from hypertension therapy
5. Hypertension associated adverse events during the course of treatment

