5. N/A

5.0 Procedures Involved

1. Study Design: Retrospective analysis of association with DNA variants with pharmacotherapy used to achieve BP control.

General Flow of Activities:

1. Patients identified via UMN AHC-IE and sent recruitment letter, consent, survey and buccal swab kit via FRA's recruitment mailing process.
 - a. An E-mail, Letter, survey information, are included along with this submission.
2. Subject collects buccal swab:

Using the collection kit consisting of two buccal swabs and two uniquely barcoded tubes the investigator, patient, or designee will remove the first buccal brush and scrape the brush end across the inside of a Subject's right cheek repeatedly (for five seconds using moderate pressure). The investigator, patient, or designee will place the brush end over the open buffer vial and press the opposite end of the swab stick to release the brush into the buffer and then close the vial. The process will be repeated on the left cheek. Each of the right and left cheek vial numbers must be recorded on the clinical review form and accountability log as right (R), or left (L).

PROTOCOL TITLE:

VERSION DATE:

3. The patients return completed consent, buccal kit, to Geneticure for sorting.
4. The signed consent form is sent to the PI ([name]) and the buccal swab in lysis buffer is sent to the University of Arizona Genomics core facility for Genotyping.
 - All genotyping is performed in a blinded manner looking at 19 single nucleotide polymorphisms.
5. \$30 sent to participant at the time the Geneticure team receives the buccal swab, consent, etc. The Geneticure team will perform any follow-up needed for participants who do not receive their payment, additional questions. Clinical questions will be forwarded to [name] as the PI
6. Research team (Fairview pharmacy residents [name] and [name]) conducts chart review and abstracts data onto CRFs
7. CRFs sent to Geneticure

Specific Study procedures:

Screening

- Identify Potential Study Subjects through AHC. Refer to the Inclusion and Exclusion Criteria sections of this protocol for a complete list of eligibility criteria.
- Obtain Written Informed Consent either in-person or via mail. Each potential study participant must be given time to review the IRB-approved informed consent form, have his/her questions answered to their satisfaction and sign the form prior to any study procedures being performed. A subject will be given a copy of the informed consent form.

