16.0 Data Management

1. Data Analysis Plan:

The Investigator is responsible to ensure the accuracy, completeness, and timeliness of reported data.

PROTOCOL TITLE:

VERSION DATE:

All data will be compiled within the Fairview system on secure servers. De-identified final data may be sent to Geneticure using a secure, password-protected Excel spreadsheet on a server that is only accessible to IRB-approved personnel and is fully auditable. The database will be validated prior to use in the study. All required data will be recorded on CRFs or paper facsimiles. Data collected within the CRFs will be supported by source documents as appropriate and may be updated to reflect the latest observations on the subjects participating in the study. Corrections to the source documentation will be made in a manner that does not obscure the original entry and will be dated and initialed by the Investigator or assigned designee. It is important for data entry to occur in a timely manner, therefore, data collected on source documents should be transferred into CRFs as soon as possible following study visits.

All data will be coded for statistical analysis (i.e. drug classes will be coded numerically and genotypes will be coded numerically). Subject's raw genetic data will be entered into the Geneticure for Hypertension algorithm. All data will be analyzed with SPSS v.20. Normality of the data will be assessed using Levene's test prior to statistical analysis and any correction for non-normal data distribution will be used. Descriptive statistics will be computed (average time for blood pressure control, average number of visits to the clinician for blood pressure control, age, height, weight, BMI, etc.).

Data will be initially analysed following the collection of samples/data from up to 600 subjects. Statistical tests will be corrected for the number of tests run (preservation of alpha). Ordinary least squares regression via univariate modelling will be used to estimate the magnitude of linearity between drug class that yielded the best blood pressure control and genetic profile of the subject. Multiple regression analysis will be performed to determine the impact of confounding variables (height, weight, age, race) on blood pressure control. For all statistical analyses an alpha level of 0.05 will be used to determine statistical significance.

Missing Data

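### The objective is prediction of the successful therapy, but the plan tests association only: the algorithm's output is never compared with the charted class or with a non-genetic benchmark

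*Combined protocol and SAP*

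**What the plan says.** The Study Summary, Section 1.0 and Section 3.0 state the same aim: to assess the effectiveness of using a patient's "genes to predict which hypertension therapy is successful". Section 5.0 describes the design in weaker terms: "Retrospective analysis of association with DNA variants with pharmacotherapy used to achieve BP control".

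Five statements in the Data Analysis Plan of Section 16.0 bear on this aim:

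- Drug classes and genotypes are coded numerically, and the subject's "raw genetic data will be entered into the Geneticure for Hypertension algorithm". No analysis of the algorithm's output follows.
- Univariate ordinary least squares is used to "estimate the magnitude of linearity between drug class that yielded the best blood pressure control and genetic profile of the subject".
- Covariates appear once: "Multiple regression analysis will be performed to determine the impact of confounding variables (height, weight, age, race) on blood pressure control".
- Tests are to be corrected for the number run. Neither the method nor the number is given.
- The only threshold is this: "For all statistical analyses an alpha level of 0.05 will be used to determine statistical significance".

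No section gives a measure of agreement, discrimination or accuracy, a minimum level of performance, or a non-genetic comparator. Section 2.0 describes a customary prescribing order, "typically initiating with the diuretic class", but no analysis uses it as a reference.

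**The concern.** A prediction claim and an association claim need different evidence. Association asks whether genotype and drug class are related at all. Prediction asks whether knowing the genotype names the right class more often than could be done without it. A test of association with several hundred subjects can be clearly significant while the gain in correct predictions is small or nil.

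As the plan stands, a significant regression could be reported as showing that genes predict therapy. The reader could not tell whether the algorithm did better than age, sex, race and weight, or than always naming the usual first-line class. The protocol says the panel is meant to let a clinician guide therapy, so this is the claim most likely to be carried forward.

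**Working it through.** **The plan's own planning figure.** Section 16.0 (Power Analysis) takes the smallest-effect variant, WNK-1: mean arterial pressure 97.6 v 100.8 mmHg, pooled SD 12, alpha 0.05, power 0.80, 300 per group. The formula n = 2(z₀.₉₇₅ + z₀.₈₀)²(SD/Δ)² gives 2 × (1.960 + 0.842)² × (12/3.2)² ≈ 221 per group. The stated 300 is therefore not reproduced; it gives about 90% power. That is a separate matter. For this point, the calculation compares pressure between genotypes within one drug class, so it does not size a test of prediction.

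**Smallest correlation that reaches significance.** N = 600 (Section 16.0, initial analysis). The formula is r = t/√(t² + N − 2).

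- Uncorrected, two-sided 0.05: t = 1.964, so r = 1.964/√(3.857 + 598) = 0.080 and R² = 0.64%.
- Bonferroni over the 18 SNPs listed in Section 4.0 (an assumption, as no method is named): alpha = 0.05/18 = 0.0028, t ≈ 3.00, r = 0.122, R² = 1.5%. Using 17 or 19 tests instead gives r = 0.121 or 0.123.

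**What the planning effects amount to.** With equal groups, R² = d²/(d² + 4) and AUC = Φ(d/√2).

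- WNK-1: d = 3.2/12 = 0.267, R² = 1.7%, AUC = 0.575.
- Beta-1 receptor, position 49 (97 v 102 mmHg, SDs 12.4 and 11.5, root-mean-square SD 11.96): d = 0.42, R² = 4.2%, AUC = 0.62.

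Both describe how well mean arterial pressure separates two genotypes within one class. They indicate the size of single-variant effects, not the accuracy of the panel.

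**Significance without predictive gain.** The documents give no class shares, so this is an illustration. It assumes two genotype groups of 300, class reduced to commonest v other, a commonest-class share of 50%, 60% or 70%, and a 12-point difference in its use between genotypes. Power = Φ((Δ − 1.96·SE₀)/SE₁), where SE₀ is the pooled and SE₁ the unpooled standard error.

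| Commonest-class share | Use by genotype | Power, uncorrected 0.05 | Correct using genotype | Correct always naming commonest class |
|---|---|---|---|---|
| 50% | 56% v 44% | 0.84 | 56% | 50% |
| 60% | 66% v 54% | 0.85 | 60% | 60% |
| 70% | 76% v 64% | 0.90 | 70% | 70% |

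At 60% and 70% the commonest class is the best guess in both genotype groups, so genotype changes no prediction. With Bonferroni over 18 tests, 80% power needs a difference of about 15.3 points (60% share) or 14.4 points (70% share). Both groups still stay above 50%, so the gain is still zero. At a 50% share the gain is real. Significance alone does not separate these cases.

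**The case against.** **This is an association study.** The title asks about association with response and uses prediction only to describe the algorithm. The design is labelled a retrospective association study, and the power section calls it pilot or feasibility work. This stands in part: the mismatch lies in the objective as much as in the analysis, so rewording the objective is a valid remedy. It does not remove the mismatch, because the objective and primary endpoint still speak of prediction.

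**0.05 is a significance level, not a success rule.** Correct. A reader might infer that the plan declares prediction proven at p < 0.05; no sentence says so. The plan also promises a multiplicity correction, and the regression would estimate a magnitude. But no magnitude is named as sufficient, and nothing else is offered to decide on, so significance is the criterion by default.

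**Covariates are already modelled.** They are, but with blood pressure control as the outcome. No model of drug class with and without genetic information is specified.

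**Uneven class use makes agreement with the chart high by default.** This stronger reading is tempting, and the documents do not support it. They give no class shares and plan no agreement analysis. Section 9.0 allows five classes alone or in combination, so agreement is not yet defined. In the planned regression, an uninformative profile has an expected association of zero whatever the split. The commonest class matters only as a benchmark once agreement is reported.

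**Single-variant figures understate a panel.** True. WNK-1 was chosen in the power section as the smallest effect, and neither AUC above applies to the full algorithm.

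**Conclusion.** The concern holds in a limited form. The stated objective is prediction; the stated analysis is association; the algorithm's recommendation is compared with nothing; and no non-genetic benchmark is given. At N = 600, significance needs only r of about 0.08 (R² 0.6%), or about 0.12 (R² 1.5%) under an assumed Bonferroni correction over 18 SNPs. A significant result therefore need not mean useful prediction, and under assumed class shares of 60% or 70% it can come with no gain at all.

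None of this shows that the panel lacks predictive value, which a reader might infer from the small R² values. They are the least that would be significant, not what will be observed. The gap should be closed before the data are seen, because a benchmark chosen afterwards carries less weight. The data themselves remain usable.

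**What to change.** In Section 16.0, add a pre-specified comparison of the algorithm's recommended class with the charted class or classes at control:

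- Handle multi-class regimens as one yes/no outcome per class, and state in advance when a recommendation counts as agreeing with a combination.
- For each class, fit a non-genetic model (age, sex, race, weight) with and without the algorithm's recommendation. Report the gain in AUC with a bootstrap 95% CI.
- Report percent agreement and kappa beside the agreement obtained by always naming the commonest class. That class is a constant, so it serves as a reference rule and not as a covariate.
- Base any statement about prediction on the size and interval of the gain. A likelihood-ratio test alone would repeat the present problem. Report SNP and least-squares p-values as association only.
- State the limit of the claim. The Study Summary and Section 4.0 restrict the study to patients with a history of control, so the charted class partly reflects prescribing order. The result can support concordance with successful regimens, not proof that the predicted class works better.

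If this is not wanted, reword the objective and primary endpoint to association.

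The variables are already collected (Section 5.0, Chart Review), so the cost is protocol text, rules for combinations and a few extra model runs. A positive prediction claim becomes harder to reach. As a guide to precision, suppose algorithm and benchmark differ in correctness for 20% to 50% of 600 patients (assumed). The 95% half-width for the difference in agreement is then 1.96 × √(0.20/600) = 3.6 points to 1.96 × √(0.50/600) ≈ 5.7 points. Intervals of that width are acceptable in a pilot.

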4.0 Study Intervention(s)/Investigational Agent(s)

1. Description: A multigene panel comprised of genes with known functionality in the heart, vasculature, and kidney, that are known to influence BP. This study will be performed as a retrospective study on patients within the Fairview Health System. Patients will be those who have been previously diagnosed with hypertension and have a history of blood pressure control (<140/<90 for two consecutive office measures. The study will involve collection of a buccal swab (can be done at the patient’s home, by the patient) and a clinical chart review of the patient’s hypertension and medication history. From the buccal swab we will assess 18 SNPs in 11 genes (2) SNPs in ADRB1, (2)

PROTOCOL TITLE:

VERSION DATE:

SNPs in ADRB2, (1) in SCNN1A, (1) in ADD1, (2) in SLC12A3, (3) in WNK1, (1) in ACE, (3) in AGT, and (1) each in AGTR1, CYP2D6*4 and REN) with known functionality in the liver, heart, vasculature, and kidney.

2. Drug/Device Handling: The device used for sample collection is a buccal swab kit that gently removes cells from the inside of the cheek. The Geneticure kit contains two buccal brushes and two tubes of lysis buffer. The patient swabs their left cheek and deposits the end of the swab in the lysis buffer, then does the same for the right cheek. This swab is placed (by the patient) in lysis buffer (a small tube) and shipped to the study site, if collected off site. The swab is then shipped to the University of Arizona Genomics core facility for DNA extraction, quantification, and assessment of the genes listed above. The study is retrospective in nature and the DNA assessment will not influence prescribing, i.e. no drugs will be changed based on this analysis for the patients. No identifying information will EVER accompany the kit to the genetic testing facility.
3. IND/IDE: In-vitro diagnostic device and exempt from IDE.
4. Biosafety: N/A

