17 genes that are contained within the Geneticure panel for hypertension treatment. Several of the genes with large effects can demonstrate statistical differences at relatively small sample sizes. For instance position 49 of the beta-1 adrenergic receptor demonstrates a functional genotype mean arterial blood pressure of 97mmHg (SD of 12.4mmHg) with beta-blocker therapy and the non-functional genotype demonstrates a mean arterial blood pressure of 102mmHg (SD of 11.5mmHg) with this same therapy. A power calculation based on this site of the beta-1 adrenergic receptor would yield a sample size per group needed of 109 for an alpha level of 0.05 and a power of 0.80 (not correcting for multiple comparisons) (table 1). Based on these results we can determine that the gene with the smallest effect from this previous smaller study (specifically that encoding WNK-1, rs2107614) will determine the approximate sample size needed to observe an effect, if an effect exists, for the panel as a whole in this prospective trial. Data from our phase-I trial demonstrates a mean arterial blood pressure of 97.6mmHg with diuretic therapy in the functional genotype group of WNK-1 and a mean arterial blood pressure of 100.8mmHg (Pooled SD = 12) with diuretic therapy in the non-functional genotype group for this site of WNK-1. Without correcting for multiple comparisons, one can determine that a per-group sample size of 162 individuals would be needed for 80% power with an alpha of 0.01. Using an alpha of 0.05 and a power of 0.80 we have estimated that we will need 300 subjects per group to observe a significant difference, where one exists. Based on possible retention of 70% of subjects who initially enroll, we will seek to recruit up to 2000 subjects for the study.

Concomitant Medications/Treatment/Procedures

This study protocol does not require change to any existing treatments or those prescribed during the course of the study by the Investigator or any other provider whom the subject sees for any medical reason. Outside of eligibility screening, there are no clinical evaluations planned as part of this study.

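### The study is sized on genotype differences within one drug class, and no genotype-by-drug-class term on blood pressure is specified, so neither the stated power nor any listed model addresses which therapy works for which genotype

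*Combined protocol and SAP*

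**What the plan says.** The primary aim in section 3.0 concerns the "use of a patient’s genes to predict which hypertension therapy is successful". One of its two primary measures is change in blood pressure from baseline to control.

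The power analysis in section 16.0 uses two examples from the group's earlier data, each confined to users of one class:

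- ADRB1, position 49: "functional genotype mean arterial blood pressure of 97mmHg (SD of 12.4mmHg) with beta-blocker therapy", while "the non-functional genotype demonstrates a mean arterial blood pressure of 102mmHg (SD of 11.5mmHg) with this same therapy".
- WNK-1, rs2107614: "mean arterial blood pressure of 97.6mmHg with diuretic therapy in the functional genotype group of WNK-1", against "100.8mmHg (Pooled SD = 12) with diuretic therapy in the non-functional genotype group for this site of WNK-1".

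No off-class, untreated or baseline values are given for either variant. Section 4.0 describes the test as "A multigene panel comprised of genes with known functionality in the heart, vasculature, and kidney, that are known to influence BP".

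The data analysis plan in section 16.0 is wider than these examples. It codes drug classes and genotypes as numbers and uses ordinary least squares to relate the class that gave the best control to the genetic profile. A separate multiple regression on blood pressure control names height, weight, age and race. It names neither genotype nor drug class. Section 9.0 admits users of five classes, alone or in combination.

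**The concern.** Asking which therapy works for which genotype is asking whether the genotype difference in response changes with the drug. A difference between genotypes among users of one class does not show that. It may be prognostic, meaning present on any therapy, or predictive, meaning specific to that class. Only a predictive variant could support choosing a drug by genotype. The protocol itself says that the panel genes influence blood pressure, so a purely prognostic difference on treatment is plausible.

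If the power figure and the models do not target the difference between classes, a positive result could be reported as support for the algorithm without bearing on it. A null result could be over-read because the study was described as having 80% power.

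**Working it through.** **Inputs** (section 16.0 unless noted). ADRB1: 97 vs 102 mmHg, SDs 12.4 and 11.5, so the difference is 5 and the pooled SD is √((12.4² + 11.5²)/2) = 11.96. WNK-1: 97.6 vs 100.8 mmHg, SD 12, difference 3.2. Initial analysis at up to 600 subjects; up to 2,000 recruited with 70% retention. Sidedness is not stated; two-sided tests and a normal approximation are assumed below.

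**1. The plan's own figures.** n per group = 2[SD(z₁₋α/₂ + z₁₋β)/δ]².

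- ADRB1, α 0.05, power 80%: 2(11.96 × 2.80/5)² gives 90. The plan states a "sample size per group needed of 109 for an alpha level of 0.05 and a power of 0.80 (not correcting for multiple comparisons".
- WNK-1, α 0.01, power 80%: 2(12 × 3.417/3.2)² gives 329. The plan says "a per-group sample size of 162 individuals would be needed for 80% power with an alpha of 0.01".
- WNK-1, α 0.05, power 80%: 2(12 × 2.80/3.2)² gives 221. The plan states 300, which would give 90% power.

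None of the three is reproduced. That is a separate matter and this point does not depend on it. What matters here is that all three are sizes for a within-class contrast.

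**2. What the within-class contrast detects.** Suppose WNK-1 raises MAP by 3.2 mmHg on every therapy, so the true class-specific effect is 3.2 − 3.2 = 0. At 300 per group, SE = 12√(2/300) = 0.980 and 3.2/0.980 = 3.27, so the within-class test is significant with probability Φ(3.27 − 1.96) ≈ 0.90. For ADRB1 at 109 per group, SE = 11.96√(2/109) = 1.62 and 5/1.62 = 3.09, giving about 0.87. A test of the genotype-by-class interaction would be significant 5% of the time in both cases.

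**3. Power for the interaction.** The interaction is the on-class contrast minus the off-class contrast. With n per cell in four equal cells, SE = SD√(4/n). For WNK-1, with all 3.2 mmHg drug-specific (an assumption):

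| Subjects | Per cell | SE | 3.2/SE | Power |
|---|---|---|---|---|
| 600 | 150 | 1.960 | 1.63 | 37% |
| 1,200 | 300 | 1.386 | 2.31 | 64% |
| 2,000 × 0.70 = 1,400 | 350 | 1.283 | 2.49 | 70% |

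For 80% power, n per cell = 4(12 × 2.80/3.2)², which gives 442, or 1,768 in total. If only three quarters or half of the difference is drug-specific, the figures are 785 per cell (3,140) and 1,766 per cell (7,064). ADRB1 is easier: 73% power with 600 subjects, and 180 per cell (720) for 80%. At half the difference it needs 719 per cell (2,876).

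**4. Does a listed analysis fill the gap?** The best-class regression treats an unordered class as a quantity, so its slope depends on which class receives which number. A variant that favours a class with a middle code over those at either end could show no slope. Section 16.0 does not say how a patient on a combination is coded. Blood pressure enters only through the choice of best class.

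The regression is also not immune to prognostic effects. Section 2.0 describes stepwise care: typically a diuretic first, then an ACE inhibitor or ARB added, then a beta-blocker if control is still not reached. A variant that raises pressure on everything moves carriers to later steps, so class at control can track genotype without any drug-specific effect.

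**The case against.** The strongest reply is that the two within-class examples are earlier data used for sizing, not the analysis plan. A reader might infer from them that genotypes will be compared only among users of the matching class, and that the 90% in step 2 is the study's rate of false predictive claims. The documents support neither inference. Section 5.0 describes an association of variants with the therapy used to reach control, and the section 16.0 regression covers all classes. The within-class t-test behind the 90% is not a listed analysis. In a comparison of best class with genotype, a variant that raises pressure equally on all therapies does not by itself favour one class. This part of the reply stands, subject to the coding and stepwise-care problems above.

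Second, change from baseline is a primary measure, and a constant genotype effect cancels in a change score. That holds for a fixed treatment and an unselected sample. Here the end of the interval is control itself, and section 4.0 restricts the cohort to patients with a history of control. A higher starting pressure then tends to require a larger fall, and no baseline adjustment is named. The endpoint helps but does not settle the matter.

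Third, an interaction term is no clean cure. Classes are not randomised and may be combined, patients are selected on control, and the cells may be small. All of that stands and limits what the remedy can deliver. So does the context: this is a retrospective association study, described as pilot or feasibility work, whose results do not alter prescribing.

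**Conclusion.** The concern holds as a mismatch between the question, the sizing and the models. The quoted power belongs to a prognostic-or-predictive contrast within one class. The one genotype model that spans classes does not model blood pressure by genotype and class, and its linear coding of class is not interpretable. No listed analysis estimates the quantity that a claim of predicting response to a class would need.

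For the variant that the plan treats as its smallest effect, the relevant power is about 37% at the planned initial analysis and would stay below 80% at full recruitment with 70% retention. These figures assume equal cells, SD 12 and a fully drug-specific effect. Genotype frequencies and class mix are not in the documents; unequal cells and combination therapy would lower the power further. The calculations use on-treatment MAP because the documents give no SD for baseline-adjusted change, which could be smaller. This should be corrected before analysis, but it does not invalidate an exploratory association study.

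**What to change.** In section 16.0:

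1. For any claim that a variant predicts response to a class, prespecify a regression of change in blood pressure on baseline blood pressure, the listed covariates (height, weight, age, race), genotype, on/off that class, and genotype × on/off class. Use enrolled patients not taking the class as the off-class group. The interaction coefficient carries the claim and falls under the multiplicity correction already planned.
2. Label within-class genotype contrasts as descriptive.
3. State that the 80% power applies only to a within-class difference. Either add the interaction power with its assumed cell sizes, or say that the study is not powered for the interaction.
4. List confounding by non-random prescribing, combination therapy and selection for control as limitations that the interaction does not remove.

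The change is to the analysis text. Section 9.0 admits five classes, so off-class patients should be present, though how many is unknown until class mix and genotype counts are tabulated. Baseline pressure is already needed for the change endpoint. The cost is a less favourable power statement. Powering the interaction at 80% would be more than a wording change, since it would take about 1,768 analysable subjects under the assumptions above.

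### The stated 0.80 power at 300 per group is for on-treatment MAP in one SNP contrast among diuretic users, which is neither primary endpoint; control read as yes/no falls short of 80%, and change from baseline may or may not reach it

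*Combined protocol and SAP*

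**What the plan says.** Section 3.0 (Study Endpoints/Events/Outcomes) lists two primary measures: "Level of blood pressure control (<140/<90" and "Change in blood pressure from baseline to control".

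Section 16.0 (Data Management, Power Analysis) uses neither. It takes the smallest effect seen in an earlier, smaller study: "the gene with the smallest effect from this previous smaller study (specifically that encoding WNK-1, rs2107614) will determine the approximate sample size needed". Diuretic users with the functional genotype averaged 97.6 mmHg; for those with the non-functional genotype the plan gives "a mean arterial blood pressure of 100.8mmHg (Pooled SD = 12) with diuretic therapy". It then gives two sizes for this contrast. The first is "a per-group sample size of 162 individuals would be needed for 80% power with an alpha of 0.01". The second, which is the one adopted, is "Using an alpha of 0.05 and a power of 0.80 we have estimated that we will need 300 subjects per group". The contrast is said to set the size for more than this SNP: it "will determine the approximate sample size needed to observe an effect, if an effect exists, for the panel as a whole".

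No control rate, SD of change, baseline pressure or correlation between baseline and on-treatment pressure is given for the study population. Neither primary endpoint has a power statement of its own.

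**The concern.** The endpoints and the sizing variable may all come from the same cuff readings, but that does not give them the same power. Cutting a continuous pressure at a threshold discards information, so a yes/no endpoint needs more subjects for the same underlying shift. A change score has an SD that depends on the baseline correlation; it can be larger than, equal to or smaller than the SD of a single reading.

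What is at stake is how a null result would be read. If control showed no association, the plan as written would let the result pass as evidence from a study with 80% power. The claim for the whole panel adds to this, because the calculation concerns one SNP in users of one drug class.

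**Working it through.** **Inputs from section 16.0.** MAP 97.6 and 100.8 mmHg, so the difference is 3.2; pooled SD 12; standardised difference 3.2/12 = 0.267; alpha 0.05 (sidedness not stated; two-sided used here); 300 per group.

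**1. The plan's own figure (MAP).** n per group = 2 × (SD/difference)² × (z for alpha + z for power)².
- 80% power: 2 × (12/3.2)² × (1.960 + 0.842)² = 220.7, so 221. The plan says 300.
- 90% power: 2 × (12/3.2)² × (1.960 + 1.282)² = 295.5, so 296.
- Power at 300: SE = 12 × √(2/300) = 0.980; 3.2/0.980 = 3.27; Φ(3.27 − 1.96) = 0.904.

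So 300 per group is about 90% power for MAP. The other stated size does not reproduce either: 80% power at two-sided alpha 0.01 needs 329, not 162. The stated sizes also rise from 162 to 300 as alpha is relaxed from 0.01 to 0.05, which is the wrong direction.

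**2. Control as yes/no.** Assumption: a normal pressure with the same shift of 0.267 SD, cut at a single threshold. For a nominal control rate p, the two group rates are Φ(Φ⁻¹(p) ± 0.133). Power = Φ{[p1 − p2 − 1.96 √(2p̄(1 − p̄)/n)] / √([p1(1 − p1) + p2(1 − p2)]/n)}.

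At p = 52% and n = 300: p1 − p2 = 0.5728 − 0.4669 = 0.1059; pooled SE 0.0408; unpooled SE 0.0406; (0.1059 − 0.0800)/0.0406 = 0.64; power 0.739.

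| Assumed control rate | Group rates | Power at 300 per group | n per group for 80% |
|---|---|---|---|
| 52% | 57.3% v 46.7% | 74% | 348 |
| 70% | 74.5% v 65.2% | 70% | 386 |
| 80% | 83.5% v 76.1% | 62% | 454 |
| 90% | 92.1% v 87.5% | 48% | 653 |

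The most favourable cut lies midway between the means, at 99.2 mmHg (55.3% v 44.7%). Power there is 74%, so no control rate brings this endpoint to 80%. If 140/90 is taken as MAP (140 + 2 × 90)/3 = 106.7 mmHg, also an assumption, the rates are 77.5% v 68.8%, power is 68% and 402 per group are needed.

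The 52% is the proportion controlled among US adults with hypertension in section 2.0, where only 75% are treated. Section 9.0 requires every subject to be on treatment, so 52% is only an illustrative value.

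**3. Change from baseline.** Assumptions: equal baseline means, SD 12 at both times, correlation r. SD of change = 12 × √(2(1 − r)).

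| r | SD of change | Power at 300 per group |
|---|---|---|
| 0 | 17.0 | 64% |
| 0.2 | 15.2 | 73% |
| 0.32 | 14.0 | 80% |
| 0.5 | 12.0 | 90% |
| 0.7 | 9.3 | 99% |

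The break-even SD is 3.2 × √150 / 2.802 = 13.99, so r = 1 − (13.99/12)²/2 = 0.32.

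**4. Who counts towards the 300.** The contrast applies only to diuretic users, while section 9.0 admits five drug classes. If, as an assumption, half of 600 subjects take a diuretic and the genotype groups are equal, there are 150 per group, and power for MAP itself is about 64%.

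**The case against.** The strongest objection is about the endpoint. Section 3.0 speaks of the level of control, and the only inferential methods in section 16.0 are least-squares and multiple regression; no logistic model or test of proportions is named. If level means achieved pressure, on-treatment MAP is close to that endpoint and 300 per group gives about 90% power. This stands as a real ambiguity. The <140/<90 threshold makes yes/no the better reading, but not a certain one, so the shortfall for control is conditional on it.

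The plan also calls itself a pilot or feasibility study and says that accurate inputs for detailed power calculations were not available. That excuses imprecise inputs. It does not excuse a power figure that belongs to a different endpoint, and a power and a size are stated all the same.

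Recruitment may run to 2000, and 70% retention would leave 1400, more than 2 × 653 = 1306. This helps only partly: section 16.0 sets the initial analysis at up to 600, and total enrolment is not the number of diuretic users.

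A reader might also infer that the control endpoint cannot vary because everyone is controlled at entry. The documents do not settle that. The Study Summary describes patients who have achieved control, section 4.0 asks only for a history of control on two consecutive office measures, and the criteria in section 9.0 do not require control. Little or no variation follows only if the population is limited to patients controlled at the time of analysis.

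**Conclusion.** The mismatch is plain on the text: the stated power belongs to neither primary endpoint. Its size depends on assumptions that the plan does not give. Read as yes/no, control has at most about 74% power at 300 per group, under a normal single-threshold model with the plan's own shift. Higher control rates lower it further. For change, the finding is an unstated assumption and not a demonstrated shortfall: a reader might infer that change is underpowered, but the documents give no correlation, and any value above about 0.32 meets 80% under the equal-SD assumption.

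A reader might also conclude that MAP should become the primary endpoint because the calculation supports it. That does not follow. The calculation does not reproduce as stated, and changing a primary endpoint is a design decision. If only controlled patients were analysed, MAP would be truncated too: cutting both distributions at 106.7 mmHg leaves a difference of about 1.7 and an SD of about 8.7, with about 65% power at 300 per group.

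**What to change.** In the Power Analysis of section 16.0:

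- State power at 300 per group separately for control and for change. Label the assumed control rate, and the assumed SD of change or baseline correlation, as assumptions, and show a range.
- Correct the MAP statement: on the given inputs 300 per group is about 90% power, and 221 per group gives 80%. State whether alpha is two-sided.
- Say in section 3.0 whether level of control is a yes/no status or the achieved pressure. Reconcile the Study Summary, section 4.0 and section 9.0 on whether subjects must be controlled.
- Say that the MAP figure applies to one SNP in diuretic users, and remove the claim that it sizes the whole panel.

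The cost is one recalculation and some rewording, with no new data or procedures. If control is yes/no, its stated power becomes less favourable.
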